Within the scope of protocol 12-DK-0097, while defining the detailed relationship between resting EE and environmental temperature, we are defining the maximum amplitude or the capacity of NST. In brief, in that protocol the range of environmental temperatures being studied (16-31°C) is that routinely encountered during daily activity, including the comfort zone¹⁴ and slightly lower. Importantly, the protocol is designed to minimize the contributions of physical activity, thermic effect of food, and behavioral changes (such as changes in body position) and standardizes the insulating properties of clothing worn for testing (clo=0.36). Thus the measured EE is expected to reflect NST in response to the environment. The protocol determines the following parameters

experimentally (see Figure 1^{1,15}): 1) the thermoneutral zone (TNZ), defined as the environmental temperature range in which EE is at a minimum and does not change with environmental temperature, 2) the shivering threshold, defined as the lowest environmental temperature before shivering occurs, and 3) the capacity for non-shivering thermogenesis, defined as the difference in EE measured at the shivering threshold and at thermoneutrality.

To our knowledge, 12-DK-0097 is providing the first rigorous measurement of the capacity for non-shivering thermogenesis in humans. In a preliminary analysis of the first subjects, a lean Caucasian cohort, EE at the shivering threshold was $17.4 \pm 3.7\%$ ($n=6$) greater than BMR. We were initially surprised by this unexpectedly large capacity for non-shivering thermogenesis, as prior publications of mild cold-induced thermogenesis found increases of only 3 to 11% (Table 1). However, we believe that the 17% value as seen in our current study is plausible for the following reasons: 1) our measurements are in the fasting state, removing any masking of facultative thermogenesis by the thermic effect of food (a phenomenon already recognized by Rubner in 1902⁹), 2) strict enforcement of no physical activity, 3) strict prohibition of postural and behavioral changes, and 4) actual measurement of the TNZ and shivering threshold, ensuring that the full span of NST is captured, compared to two fixed temperature points which were used by most previous studies. We note that a crucial innovation is the use of a relatively short time period for the EE measurements, allowing stricter control of the above variables, enabled by specialized analysis of the chamber data¹⁶.

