- 1) Propranolol 160 mg PO will reduce the resting EE measured at a temperature just above the subject's placebo shivering threshold (REE_{Low}) by greater than or equal to 5% compared to placebo REE_{Low} . If propranolol-treated subjects shiver at the low temperature, then measurement of non-shivering EE is not possible in this protocol. Propranolol will be judged to increase the shivering threshold if significantly more subjects shiver with propranolol than with placebo treatment.
- 2) Pindolol 20 mg PO will lead to a similar difference in resting EE measured at thermoneutrality ($REE_{27^\circ C}$) and REE_{Low} .
- 3) Dantrolene 100 mg PO will reduce the REE_{Low} by greater than or equal to 5% compared to placebo REE_{Low} . If dantrolene-treated subjects shiver at the low temperature, then measurement of non-shivering EE is not possible in this protocol. Dantrolene will be judged to increase the shivering threshold if significantly more subjects shiver with dantrolene than with placebo treatment.
- 4) Magnesium sulfate (50 mg/kg bolus followed maintenance infusion at 2 g/h) will reduce the REE_{Low} by greater than or equal to 5% compared to REE_{Low} .

Cohort 2

- 1) To evaluate the effect of caffeine (300 mg PO) on BMR ($=REE_{27^\circ C}$).
- 2) To evaluate the effect of Qsymia (topiramate 92 mg CR, phentermine 15 mg PO) on BMR.

- 3) To evaluate the effect of phentermine (37.5 mg PO) on BMR.
- 4) To evaluate the effect of topiramate (200 mg PO) on BMR.
- 5) To evaluate the effect of naltrexone (100 mg PO) on BMR.

Hypotheses

- 1) Caffeine 300 mg PO will increase BMR by greater than or equal to 5% vs placebo.
- 2) Qsymia (topiramate 92 mg CR, phentermine 15 mg) PO will increase BMR by greater than or equal to 5% vs placebo.
- 3) Phentermine 37.5 mg PO will increase BMR by greater than or equal to 5% vs placebo.
- 4) Topiramate 200 mg PO will increase BMR by greater than or equal to 5% vs placebo.
- 5) Naltrexone 100 mg PO will increase BMR by greater than or equal to 5% vs placebo.

Cohort 3 – This Cohort has completed enrollment

- 1) To compare the effects of mirabegron at 0mg, 50mg, and 200mg on BAT metabolic activity.
- 2) To compare the effects of mirabegron at 0mg, 50mg, and 200mg on BMR.

Hypotheses

- 1) Mirabegron at 50mg and 200mg PO will each increase BMR and BAT activity more than placebo.
- 2) The increases in heart rate and systolic BP after a one-time dose of 50mg will be lower than that observed using 200mg.

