Power calculation: To estimate power, we used data from 12-DK-0097. We first determined that the within-subject difference in the response in BMR within TNZ was normally distributed with a standard deviation of 2.54%. The maximum NST in 9 young healthy male subjects was $17.4 \pm 3.7\%$. With 12 subjects completing the protocol, if the true difference in the mean response to treatment is 5.0% as we hypothesized for each drug treatment, we will be able to reject the null hypothesis that this response difference is zero with probability (power) of 0.98 at an alpha of 0.05 in either Cohort. Since this study is designed to use the pharmacological agents only to test the mechanisms of NST and BMR, thus we will not compare any pharmacological interventions to each other. However, in the most conservative interpretation, multiple comparisons adjustments will only be necessary for the number of paired comparisons between drugs and placebo within each Cohort. The result of such a conservative estimate of power range from 0.92 at an alpha value of 0.01 (0.05/5, the Bonferroni method) in Cohort 2 to 0.94 in Cohort 1 (alpha = 0.05/4). Even if the true difference was 3%, the power to detect with n=12 is above 0.83 in all analyses. To consider in potential dropouts (about 30%), we will recruit 16 subjects for each cohort (subjects can participate in both with a minimum of 2 weeks washout in between the studies), aiming to have 12 completers for each cohort.

In Cohort 3, the primary endpoint is the difference in detectable BAT activity (units of $\text{mL}^* \text{SUVmean}^* \text{g/mL}$) between the 0 mg and 50 mg doses of mirabegron. Based on our previous study ([name] et al., 2015), BAT activity is right-skewed and not

normally distributed, so our sample size determination is based on log BAT activity, which is normally distributed. We found that log BAT activity after treatment with 0 mg mirabegron was 0.05 ± 0.62 and after treatment with 200 mg mirabegron was 2.00 ± 0.79 . Since it is unknown what the effect of 50 mg mirabegron would be on BAT activity, we calculated a range based on lower and upper bound expectations about the reported PK/PD profile of mirabegron. For the lower bound, the 50 mg dose has been found to have a mean plasma C_{max} that is 18% of 200 mg. If there were a linear relationship between BAT activity and dose, then we would predict 50 mg to produce a mean log BAT activity of 0.36.

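### The stated powers for Cohorts 1 and 2 cannot all be right: no single SD gives both the 5% powers and more than 0.83 at 3%

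*Combined protocol and SAP*

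**What the plan says.** All the power figures for Cohorts 1 and 2 stand in one paragraph of section III.1 (Subjects and Recruitment, Power calculation).

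- **Spread.** The within-subject difference in BMR inside the thermoneutral zone is described as "normally distributed with a standard deviation of 2.54"%. The next sentence reads "The maximum NST in 9 young healthy male subjects was" 17.4 ± 3.7%, without saying whether 3.7 is an SD or a standard error.
- **Sample size.** "With 12 subjects completing the protocol" is the basis for every power.
- **5% effect, alpha 0.05.** "we will be able to reject the null hypothesis that this response difference is zero with probability (power) of 0.98"; this is given for either cohort.
- **5% effect, Bonferroni.** "The result of such a conservative estimate of power range from 0.92 at an alpha value of 0.01" (five comparisons, Cohort 2) to 0.94 at 0.05/4 = 0.0125 (four comparisons, Cohort 1).
- **3% effect.** "Even if the true difference was 3%, the power to detect with n=12 is above 0.83 in all analyses".

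The comparisons are paired, drug against placebo, and the null is zero difference. The test and its sidedness are not named. The 5% effect matches the hypotheses in section II.1, for example "Caffeine 300 mg PO will increase BMR by greater than or equal to 5% vs placebo".

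**The concern.** At a fixed n and alpha, the power of a paired test depends only on the ratio of effect to SD. The powers for 5% and for 3% are therefore tied together: once the SD is set, both follow. A fall in power to 0.92 for a 5% effect at alpha 0.01 means that the SD is large relative to 5%. With that SD, an effect of 3% cannot still have power above 0.83.

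The 3% sentence is the plan's only statement of sensitivity below the hypothesised 5%. It bears mainly on Cohort 2, which, unlike Cohorts 1 and 3, is not marked as having completed enrollment. The background in section I.3 itself cites effects below 5% for agents in that cohort: 1.4% for phentermine and 4.6% for naltrexone, both non-significant and under other dosing. Whether the design can detect effects of that order is therefore a practical question, and the paragraph gives two incompatible answers.

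**Working it through.** **Inputs** (all from the power paragraph): n = 12; effects 5% and 3%; alpha 0.05, 0.0125 and 0.01; the labelled SD, 2.54%. Assumption: two-sided paired t-test.

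**Formula.** Power ≈ P(T > t_crit), where T is noncentral t with 11 degrees of freedom and noncentrality (effect / SD) × √12. The critical values are 2.201, 2.981 and 3.106 for the three alphas. The opposite tail is negligible.

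**Step 1: try to reproduce the plan with its labelled SD.** The noncentrality is 5/2.54 × 3.464 = 6.82 for 5%, and 3/2.54 × 3.464 = 4.09 for 3%.

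| | alpha 0.05 | 0.0125 | 0.01 |
|---|---|---|---|
| 5%, stated | 0.98 | 0.94 | 0.92 |
| 5%, SD 2.54 | >0.999 | 0.999 | 0.999 |
| 3%, stated | >0.83 | >0.83 | >0.83 |
| 3%, SD 2.54 | 0.960 | 0.841 | 0.812 |

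The 5% powers are not reproduced. The 3% claim holds at two alphas and misses by about 0.02 at the third. A simulation with 400,000 replicates agrees with the 3% values (0.961, 0.841, 0.812).

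**Step 2: solve for the SD behind each stated power.**

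| | alpha 0.05 | 0.0125 | 0.01 |
|---|---|---|---|
| SD implied by the stated 5% power | 3.91 | 3.64 | 3.67 |
| Largest SD giving 0.83 at 3% | 3.24 | 2.57 | 2.49 |

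At every alpha the SD needed for the 5% figure exceeds the largest SD that the 3% figure allows. The conflict is present even at unadjusted alpha 0.05.

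**Step 3: power at 3% if the 5% powers are right.** At SD 3.6 to 3.9 it is 0.68–0.75, 0.42–0.50 and 0.38–0.46. At SD 3.7 (noncentrality 4.68 for 5%, 2.81 for 3%) the 5% powers are 0.989, 0.932 and 0.915, close to the stated ones, and the 3% powers are 0.725, 0.467 and 0.427.

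**Step 4: vary the unstated test.**

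| Test | SD implied by the stated 5% powers | Largest SD for 0.83 at 3%, alpha 0.01 |
|---|---|---|
| Paired t, two-sided | 3.64–3.91 | 2.49 |
| Paired t, one-sided | 4.02–4.38 | 2.77 |
| Normal, two-sided | 4.27–4.35 | 2.94 |
| Normal, one-sided | 4.56–4.68 | 3.17 |
| Two-sample t, two-sided | 2.80–2.91 | 1.92 |
| Two-sample t, one-sided | 3.04–3.21 | 2.10 |

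The ranges never meet. For the paired tests at SD 2.54, a one-sided test or a normal approximation makes the 3% sentence true (0.893 or higher at alpha 0.01), but the 5% powers stay at 0.999 or above, further from the stated values.

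**Step 5: effect detectable with 80% power at alpha 0.01** (two-sided paired t): 2.96% at SD 2.54; 4.19% at SD 3.59 (that is, 2.54 × √2); 4.31% at SD 3.7; 4.56% at SD 3.91.

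**A related discrepancy.** The same 17.4 ± 3.7% appears in section I with n=6 ("In a preliminary analysis of the first subjects, a lean Caucasian cohort, EE at the shivering threshold was" …) and in section III.1 with 9 subjects.

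**The case against.** The strongest reply is that the labelled SD is 2.54% and that, with it, the 3% sentence is nearly right: one analysis falls short by about 0.02, and none does under a one-sided test or a normal approximation. On that reading the 5% powers are merely understated and the study is better powered than it claims. The low 3% powers appear only if the labelled SD is replaced by one back-solved from the 5% figures. This is a fair account of one of the two readings, but it still leaves 0.98, 0.94 and 0.92 wrong, since 0.999 does not round to 0.92.

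A second reply is that two inputs were used: 3.7 for the 5% powers, which it fits within about 0.01, and 2.54 for the 3% sentence. That is plausible, but the plan does not say so, and an unannounced change of SD within one paragraph would itself need correcting. A different SD for each cohort does not help either. The 0.98 is given for both cohorts, and Cohort 2 is measured only at 27°C (section III.2-2), where the 2.54% should apply, yet its 0.92 implies 3.67%.

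Third, no decision on sample size or analysis rests on the 3% sentence, and after the trial the observed confidence interval, not planned power, shows which effects are excluded. Both points stand. They limit the consequence to what the plan promises in advance. Likewise, 6 and 9 subjects may be two data cuts, so that point is a query and not part of the power conflict.

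**Conclusion.** The concern holds. The six powers stated or implied for Cohorts 1 and 2 cannot come from one SD under any of the tests tried. Either the 5% powers are too low (they should be at least 0.999 at SD 2.54%), or the 3% claim is too high (power as low as 0.38–0.46 in the Cohort 2 Bonferroni analysis, at SD 3.6–3.9%). The documents do not settle which.

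The sample size is not undermined: for SDs from 2.54% to 3.91%, two-sided power at 5% is never below about 0.88, even at alpha 0.01. What is left undetermined is the plan's sensitivity below 5%. The headline figures assume a two-sided paired t-test with 12 completers; the existence of the conflict does not depend on sidedness or on the t versus normal choice. It should be corrected, but it does not threaten the design.

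**What to change.** Rewrite the power paragraph in section III.1:

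1. State the SD of the within-subject drug-minus-placebo difference, separately for 27°C and the low temperature if they differ, and say where it comes from. In particular, say whether 2.54% is the SD of a difference between two sessions and whether 3.7% entered any calculation.
2. Name the test and its sidedness.
3. Recompute all six powers (5% and 3%, each at alpha 0.05, 0.0125 and 0.01) from that SD.
4. Replace the blanket 3% statement with the recomputed 3% powers and, as a useful addition, the effect detectable with 80% power at each Bonferroni alpha.
5. Reconcile 6 and 9 subjects for the 17.4 ± 3.7% figure, and label 3.7 as an SD or a standard error.

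The cost is one corrected paragraph. Neither the number of subjects nor any procedure changes. Depending on the SD, either the 5% powers rise or the 3% powers fall.

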Using a different set of assumptions leads to a higher predicted effect, or the upper bound expectation. We found that after the 200 mg dose, the estimated mean peak plasma concentration (C_{max}) of mirabegron was 274 ± 64 nM based on 65% protein binding, which is 6.9x the K_i of mirabegron for the $\beta 3$ -AR (40 nM) (FDA 2012). If the 50 mg dose achieves 18% of 200 mg, then the C_{max} would be 49 nM, which is 1.2x the K_i and 2.2x the in vitro EC_{50} of 22.4 nM (Takasu et al., 2007). Therefore, 50 mg mirabegron could produce $\geq 50\%$ of the effect seen with 200 mg, or ≥ 1.00 log BAT activity. Therefore, for 50 mg mirabegron, the effect on log BAT activity ranges from 0.36 to ≥ 1.00 .

For sample standard deviation, the log BAT activity after treatment with 0 mg mirabegron was 0.05 ± 0.62 and after treatment with 200 mg mirabegron was 2.00 ± 0.79 . Assuming a linear relationship between dose and standard deviation of the outcome variable, for the 50 mg dose of mirabegron, the standard deviation for log BAT activity is predicted to be 0.66.

In summary, we are planning a study of a continuous response variable from study subjects where each acts as his own paired control. Assuming the true difference between 0 mg mirabegron and 50 mg mirabegron is 0.36 with a standard deviation of 0.66, we will need to study 28 subjects to be able to reject the null hypothesis that this response difference is 0 with $\alpha=0.05$ and power of 80%. However, if the response is 1.00, then we will need to study only 6 subjects. Given this wide range (6-28 subjects), we will plan to complete 28 subjects with an interim analysis after 12 subjects. If the results of the interim analysis suggest that the response is closer to the upper bound estimate, then we will be able to reject our null hypothesis at that point. A sample size of 12 was chosen because if 12/12 subjects show higher BAT activity with the 50 mg, then non-parametric paired comparison yields a P value of 0.001.

For these types of studies, we have experienced a screen-failure rate of 50% and a rate of detectable BAT of 66%. We therefore plan to enroll up to 84 subjects, perform Study Day A in 42, and expect 28 to complete all four study days. If we are able to complete the study after the interim analysis, then we would end up enrolling 36 subjects, initiate the screening protocol with 18, and have 12 complete all four study days.

III.2-1 Protocol design, Cohort 1 – This Cohort has completed enrollment

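### Cohort 3's 80% power with 28 subjects uses the predicted SD at 50 mg alone (0.66) as the SD of the paired 50-minus-0 mg difference; the 80% is unsupported, and the error could run either way

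*Combined protocol and SAP*

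**What the plan says.** All of this is in the combined protocol and SAP, III.1 (Subjects and Recruitment, Power calculation), unless noted. The Cohort 3 primary endpoint is the difference in detectable BAT activity between 0 mg and 50 mg mirabegron, sized on the log scale.

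- **Reference values.** "We found that log BAT activity after treatment with 0 mg mirabegron was 0.05" (SD 0.62); after 200 mg it was 2.00 (SD 0.79).
- **Lower-bound mean at 50 mg.** The text says "the 50 mg dose has been found to have a mean plasma" Cmax equal to 18% of that at 200 mg. The condition it sets is "If there were a linear relationship between BAT activity and dose", and the conclusion it draws under that condition is "then we would predict 50 mg to produce a mean log BAT activity of 0.36". A later sentence calls the same number an effect: "the effect on log BAT activity ranges from 0.36 to" at least 1.00.
- **SD.** Assuming that the SD is linear in dose, for the 50 mg dose "the standard deviation for log BAT activity is predicted to be 0.66".
- **Design and sample size.** The study is described as having "a continuous response variable from study subjects where each acts as his own paired control". Then: "Assuming the true difference between 0 mg mirabegron and 50 mg mirabegron is 0.36 with a standard deviation of 0.66", 28 subjects are needed for 80% power at alpha 0.05. A response of 1.00 would need 6.
- **Cmax in men.** I.2 (Mirabegron) gives 23.7 ng/mL for 50 mg and 158 ng/mL for 200 mg. III.1 restricts enrollment to males.
- **Status.** III.2-3 states that Cohort 3 has completed enrollment.

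**The concern.** A paired comparison is powered on the SD of the within-subject difference. The plan instead inserts the spread between men under one condition. The two are linked by the within-subject correlation, and for Cohort 3 the plan gives neither that correlation nor an SD of the difference. For Cohorts 1 and 2 the same section does use a within-subject difference SD (2.54%), so the distinction was available to the authors. Recomputing the sample size does not expose the problem, because the formula step is correct and the fault is in what was put into it.

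The 0.36 scenario alone sets the 28 subjects, and the 80% is the only statement of what the cohort could detect at that lower bound. I.2 makes later use of 50 mg depend on that dose being effective enough. If the 50 mg result is weak or null, a reader who trusts 80% power may take it as stronger evidence against an effect than the plan's figures justify.

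**Working it through.** **Method.** Paired t-test, noncentral t, two-sided alpha 0.05. The plan does not state sidedness; one-sided calculations give 21 to 23 subjects, so only two-sided reproduces 28.

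**1. Reproduce the plan.** Difference 0.36, SD 0.66, n = 28: noncentrality 0.36/0.66 × √28 = 2.89, power 0.795. The n for 80% is 27 by normal approximation and 29 by the exact t-test, so 28 is a fair reproduction. For a response of 1.00, n = 6 gives power 0.84, which also reproduces.

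**2. Where 0.66 comes from.** 0.62 + (50/200) × (0.79 − 0.62) = 0.6625. This is an SD of log BAT activity at one dose.

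**3. What the paired test needs.**

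SD of difference = √(0.62² + 0.66² − 2ρ × 0.62 × 0.66) = √(0.820 − 0.8184ρ)

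Setting this equal to 0.66 gives ρ = 0.62²/(2 × 0.62 × 0.66) = 0.47. The correlation is not in the documents, so the values below are assumptions.

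| Assumed ρ | SD of difference | Power at n = 28, difference 0.36 | Expected 95% CI half-width |
|---|---|---|---|
| 0 | 0.91 | 0.53 | 0.35 |
| 0.3 | 0.76 | 0.68 | 0.29 |
| 0.47 | 0.66 | 0.795 | 0.26 |
| 0.5 | 0.64 | 0.82 | 0.25 |
| 0.7 | 0.50 | 0.96 | 0.19 |

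Half-width = t(0.975, 27) × SD/√28, with t = 2.052.

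**4. Level or difference.** 0.18 × 2.00 = 0.36 is introduced as the mean at 50 mg, and the 0 mg mean is 0.05. Two readings, both at SD 0.66:

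- Interpolating consistently between 0.05 and 2.00: difference 0.18 × 1.95 = 0.351, power 0.77, 30 subjects for 80%.
- Taking 0.36 literally as the 50 mg level: difference 0.36 − 0.05 = 0.31, power 0.67, 38 subjects for 80%.

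**5. Cmax ratio.** 23.7/158 = 0.150, against the 0.18 used. With 15% on consistent interpolation the difference is 0.15 × 1.95 = 0.2925, and power at SD 0.66 is 0.62.

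**6. Scale.** Steps 1 to 5 keep the plan's interpolation on the log scale. The sentence that introduces it speaks of BAT activity itself, and the log base is not stated. Assuming natural logs and interpolating the back-transformed means:

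- 18%: ln(e^0.05 + 0.18 × (e^2 − e^0.05)) − 0.05 = 0.73, power 0.985 at ρ = 0.
- 15%: 0.64, power 0.95 at ρ = 0.

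Taking 18% of the back-transformed 200 mg value instead gives ln(0.18 × e^2) − 0.05 = 0.235, power 0.44 at SD 0.66. The scale therefore matters as much as the SD.

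**7. Upper bound.** At a difference of 1.00, power at n = 28 exceeds 0.99 even with ρ = 0, so the issue disappears there.

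**The case against.** The best defence is that these are openly labelled assumptions. The plan says the 50 mg effect is unknown, and its arithmetic from the stated inputs is correct. Correlations of 0.4 to 0.6 give power 0.74 to 0.89 at difference 0.36, so moderate correlation brackets the stated 80%. A reader might infer from the SD problem that Cohort 3 is underpowered. The documents do not support that: above a correlation of 0.47 the plan has more power than it claims. What survives is that 0.66 is derived as one quantity and used as another, so the 80% has no stated basis.

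A reader might also infer that 38 subjects were needed. That requires subtracting the observed 0.05 from a prediction that is proportional to dose and so implies zero at 0 mg. On that proportional model, 0.36 is itself the difference, and the upper bound of 1.00 (half of 2.00) follows the same convention. The 0.05 is also small against its SD (0.05/0.62 = 0.08). The wording does move from level to difference, but a coherent reading costs about 2 percentage points of power. Applying 15% and then subtracting 0.05 to reach 0.25 mixes the two models in the same way.

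Finally, a reader might conclude that 18% is wrong. It has no stated source or population and may come from data other than the male values. The documents show that the two figures differ, not which one applies.

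Enrollment is complete, so neither the sample size nor the estimate, test or interval changes. That limits the importance of the point but does not make the power statement correct.

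**Conclusion.** Wrong as written, with low practical impact. The SD at one dose is used as the SD of a paired difference, so 80% power with 28 subjects does not follow from the plan's figures. On the plan's log-scale interpolation with difference 0.36, power runs from 0.53 to 0.96 for assumed correlations 0 to 0.7. The direction of the error is unknown, and inadequate power is not established.

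The other two inputs are secondary. Using 0.36 as the difference costs little on a consistent reading. The unexplained gap between 18% and 15.0% would lower power to 0.62 if 15% applied, but the documents do not settle which ratio is right. These figures assume a two-sided test, SDs of 0.62 and 0.66, and interpolation on the log scale. Interpolating untransformed activity between the 0 mg and 200 mg means (natural logs assumed) gives power of at least 0.95.

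**What to change.** - Leave the sample size unchanged.
- Replace the single 80% with a power range built on the 50-minus-0 mg difference and the SD of the paired log difference. Take that SD from the previous mirabegron study if the same men were measured under both conditions; its pairs would be 0 and 200 mg, so this is a proxy for 50 mg. Otherwise state a range of correlations.
- State the scale of the interpolation and the log base.
- Reconcile the 18% Cmax ratio in III.1 with the male values in I.2, or give its source and population.
- Report the 50 mg result as an estimate with its confidence interval, so that a weak or null finding is judged by its precision.

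The cost is a rewritten power paragraph, with no extra subjects and no change to the analysis. The drawback is that one favourable number becomes a range that may look less favourable.
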